6.3.11 Management of Non-Infectious Pneumonitis

Pneumonitis is a recognized adverse effect of rapamycins (sirolimus, temsirolimus, everolimus). Numerous case reports in the literature suggest that rapamycin-associated pneumonitis is relatively non-aggressive, limited in extent and reversible upon drug discontinuation. In the largest completed phase III trial using everolimus in oncology (in patients with metastatic renal cell carcinoma), the frequency of clinically apparent pneumonitis was 14%. 4% of cases were CTC grade 3, and 0 were CTC grade 4. To date, three cases of pneumonitis have had a fatal outcome in more than 4,000 adult oncology patients treated with everolimus. All three cases were associated with overwhelming systemic infection or disease progression.

Individuals participating in this trial will be questioned at each study visit as to the presence of new or changed pulmonary symptoms consistent with lung toxicity. If an investigator suspects a patient may be developing pneumonitis, the patient should be managed according to Table 5. Investigations such as pulmonary function tests. CT chest and referral to a pulmonologist should be considered.

Table 5 Management of non-infectious pneumonitis

Worst Grade	Required Investigations	Management of	Study Treatment Dose Adjustment
Pneumonitis		Pneumonitis	
Grade 1	CT scans with lung windows and pulmonary function testing including: spirometry, DL _{CO} , and room air O ₂ saturation at rest. Repeat CT scan at least every 12 weeks until return to within normal limits.	No specific therapy is required	Administer 100% of study treatment dose.
Grade 2	CT scan with lung windows. Consider pulmonary function testing including: spirometry, DL _{CO} , and room air O ₂ saturation at rest. Repeat CT scan at least every 4-12 weeks until return to within normal limits. Consider bronchoscopy with biopsy and/or BAL	Symptomatic only. Consider corticosteroids if symptoms are troublesome.	Reduce study treatment dose by 1 dose level until recovery to ≤ Grade 1. Study treatment may also be interrupted if symptoms are troublesome. Patients will discontinue study treatment if they fail to recover to ≤ Grade 1 within 3 weeks.
Grade 3	CT scan with lung windows and pulmonary function testing including spirometry, DL_{CO} , and room air O_2 saturation at rest. Repeat at least every 4-8 weeks until return to within normal limits. Bronchoscopy with biopsy and/or BAL is recommended.	Consider corticosteroids if infective origin is ruled out. Taper as medically indicated.	Hold treatment until recovery to ≤ Grade 1. May restart study treatment within 3 weeks at a reduced dose (by one level**) if evidence of clinical benefit.
Grade 4	CT scan with lung windows and required pulmonary function testing including spirometry, DL _{CO} , and room air O ₂ saturation at rest. Repeat at least every 4-8 weeks until return to within normal limits. Bronchoscopy with biopsy and/or BAL is recommended if possible.	Consider corticosteroids if infective origin is ruled out. Taper as medically indicated.	Discontinue treatment.

6.3.12 Follow-Up for Toxicities

Patients whose treatment is interrupted or permanently discontinued due to an adverse event or abnormal laboratory value suspected to be related to study treatment must be followed at least weekly until the adverse event or abnormal laboratory resolves or returns to grade 1. If a patient requires a dose delay of \geq 6 weeks from the intended day of the next scheduled dose, then the patient must be discontinued from the study.

All patients will be followed for adverse events and serious adverse events for 28 days following the last dose of study drug. Beyond these 28 days, any serious adverse events that are suspected to be related to the study drug that are ongoing at the follow-up call will continue to be monitored for an additional next 8 weeks (56 days) or until the event resolves. Any changes in medication/therapy given during the follow-up period of 28 days will be recorded on the CRF.

7. Description of Study Procedures

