6.3.10 Dosing Modifications In Case of Treatment Related Toxicities

Table 3 Criteria for dose modification/re-initiation in case of toxicity suspected to be related to study treatment

Toxicity	Actions
Pneumonitis	See Table 5
Hyperlipidemia and/or hypertriglyceridemia	Any grade: Treat according to best clinical practice. No specific dose reductions are needed.
Hyperglycemia	Any grade: Treat according to best clinical practice. No specific dose reductions are needed.
Stomatitis	Grade 2: Interrupt study drug until resolution to ≤ grade 1. Restart at same dose. Grade 3: Interrupt study drug until resolution to ≤ grade 1. Reintroduce study drug at the next lower dose level**. Discontinue study drug if stomatitis does not recover to ≤grade 1 within 4 weeks. Grade 4: Discontinue study drug

Other toxicities	Grade 2 and 3: Interrupt administration until resolution to ≤grade 1. Restart at same dose.
	Grade 4: Hold study drug until recovery to ≤ grade 1. Reintroduce study drug at the lower dose level**, if available.
Toxicity requiring interruption for > 6 weeks	Permanently discontinue treatment.
No specific dose adjustments are recommended for Grade 1 toxicity. However, physicians should always	

manage patients according to their medical judgment based on the particular clinical circumstances.

**To determine the next lowest dose level, please refer to Table. 5.

Table 4 Dose modification guidelines for hematologic toxicities

Toxicity	Actions		
Thrombocytopenia Platelet Count	 ≥ 75000/mm³: No change 50000/mm³ to 75000/mm³: Hold study drug until recovery to ≥ 75000/mm³. Reintroduce study drug at the same dose level < 50000/ mm³: Hold study drug until recovery to ≥ 75000/mm³. Reintroduce everolimus at the next lower dose level, if available 		
Absolute Neutrophil Count (ANC)	 ≥ 1000/ mm³: No change 500/mm³ to 1000/ mm³: Hold study drug until recovery to ≥ 1000/mm³. Reintroduce study drug at the same dose level < 500/ mm³: Hold until recovery to ≥ 1000/ mm³. Reintroduce everolimus at the next lower dose level, if available. 		
Febrile Neutropenia	Hold further dosing until ANC ≥ 1250/mm ³ and no fever. Then resume dosing at the next lower dose level** if available.		
Toxicity requiring interruption for >6 weeks	Permanently discontinue treatment.		
Physicians should always manage patients according to their medical judgment based on the particular clinical circumstances.			

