7.7.3 Other Permitted Study Drug Adjustments

Standard dosing modifications will be made as described in Section 6.2.

For patients who are unable to tolerate the protocol-specified dosing schedule, dose adjustments are permitted, as described in Tables 3, 4, and 5, in order to keep the patient on study drug. In addition, if any surgery is planned, trial therapy should be interrupted one week prior to surgery and should be re-started as soon as possible after wound healing.

Dose modifications initiated by the site investigator (such as in response to a toxicity or safety lab level) will not require an everolimus PK level, unless the duration of the change lasts more than two weeks. If this was to occur, and a PK sample needed to be collected, the sample should be true trough. A true trough level is ~24 hours (+/- 4 hours) after the last dose was taken, and after 4 days of consistent dosing.

If treatment is interrupted due to toxicity, study drug should not be resumed until recovery to grade ≤ 1 is achieved. If recovery takes 6 weeks or more, the patient should be discontinued from the study. If recovery takes less than 6 weeks, study drug can be reintroduced at the initial dose or a lower dose level depending on the toxicity type and grade (see Tables 3 and 4). These changes must be recorded on the Dosage Administration Record and Dose Adjustment Log CRFs, as appropriate.

Dose adjustments (reduction, interruption, or possible dose re-escalation to starting dose) may also occur based on safety findings. All doses taken by the patient and all dose changes during the study must be recorded on the CRFs. Dose adjustments will also be made in the placebo group according to the placebo adjustment protocol.

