7.7.6 Study Drug Interruption or Discontinuation

An intent to treat approach will be used. All data acquired prior to termination for the reasons outlined below will be included in the primary analysis unless patient withdraws consent. Every effort will be made to conduct a final study visit with the participant and participants will be followed clinically until, if applicable, all adverse events resolve.

The term "interruption" refers to a patient stopping the study medication during the course of the study, but then re-starting it at a later time in the study (as determined by their study doctor).

The term "discontinuation" refers to a patient's premature and permanent withdrawal from the study treatment. The reason for discontinuation from treatment will be recorded. The patient may discontinue participation in the study for any of the following reasons:

- 1. adverse event(s)
- 2. abnormal laboratory value(s)
- 3. abnormal test procedure result(s)
- 4. protocol deviation
- 5. subject withdrew consent
- 6. Withdrawal by the investigator
- 7. lost to follow-up
- 8. administrative problems
- 9. intercurrent illness or event that precludes further visits to the study site or ability to evaluate disease (e.g.-mental status change, large pleural effusion).
- 10. death

If a patient has discontinued the study drug due to an unacceptable adverse event or an abnormal laboratory value, he/she should not have withdrawal of consent recorded as the reason for discontinuation. Instead, the reason for discontinuation must be recorded as due to adverse event or abnormal laboratory value.

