All patients must have evaluations for 28 days after the last dose of study treatment. Participants that have ongoing adverse events at the 28 day follow-up visit will continue to be followed for an additional 8 weeks (56 days) to record any SAEs that are suspected to be related to study drug. Patients lost to follow up should be recorded as such on the CRF. Patients who discontinue study drug before completing the study should be scheduled for a visit as soon as possible, at which time all of the assessments listed for End of Treatment visit will be performed. At a minimum, all patients who discontinue study treatment, including those who refuse to return for a final visit, will be contacted for safety evaluations during the 28 days following the last dose of study drug. Patients will also be asked a series of neurocognition follow-up questions by phone and will complete the CBCL and DCDQ at the final follow-up call.

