7.7.7 Withdrawal from the study and study evaluation completion

Patients may voluntarily withdraw from the study or be dropped from it at the discretion of the investigator at any time.

As a general rule, if a patient discontinues study drug and later is withdrawn from the study, the reasons for study evaluation completion may include the following:

- Protocol deviation
- Subject withdrew consent
- Lost to follow-up
- Death
- Use of non-study systemic anti-PTEN therapy
- Administrative problems

For patients who are lost to follow-up, the investigator should show due diligence by documenting in the source documents steps taken to contact the patient, e.g., dates of telephone calls, registered letters, etc.

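### Sections 6.3.12 and 7.7.3 remove patients from the study at six weeks of toxicity delay, where Tables 3 and 4 only stop treatment; this gives up Month 6 testing that the intention-to-treat comparison needs

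*Combined protocol and SAP*

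**What the plan says.** **Toxicity rules.** Tables 3 and 4 (section 6.3.10) have a row headed "Toxicity requiring interruption for > 6 weeks", and the action is to end treatment permanently. For a dose delay of six weeks or more, section 6.3.12 says "then the patient must be discontinued from the study". Section 7.7.3, which refers sites to Tables 3 and 4, says "If recovery takes 6 weeks or more, the patient should be discontinued from the study".

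**Terms.** Section 7.7.6 defines discontinuation as "premature and permanent withdrawal from the study treatment". Section 7.7.7 treats leaving the study as a later, separate step: "if a patient discontinues study drug and later is withdrawn from the study".

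**After an early stop.** Section 7.7.6 says "Patients who discontinue study drug before completing the study should be scheduled for a visit as soon as possible", with all End of Treatment assessments at that visit. After that come 28 days of safety contact and neurocognition questions by phone, and patients "complete the CBCL and DCDQ at the final follow-up call". The 28-day visit in section 4.7 lists history, medications and the DOTES. Section 4.3 requires every on-site visit, Months 3 and 6 included, and makes a missed one grounds for termination. It does not mention patients who are off drug.

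**Analysis.** Sections 7.7.6 and 17 claim intention to treat. Section 17 handles attrition under missing at random (MAR) and singles out the 6-month group difference.

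**Blinding.** Sections 4.3 and 7.6 break the code at early termination, whereas section 4.7 permits unblinding after the 28-day visit. Section 7.9.1 requires blind evaluators for the CGI scales and the ADOS-2.

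**The concern.** The protocol has separate terms for stopping drug and leaving the study, but its six-week rules do not keep them apart. One toxicity leads to two instructions. The small gap between at least six and more than six weeks matters only at exactly six weeks. The difference between study and treatment is the real one.

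A patient removed under 6.3.12 or 7.7.3 has no scheduled Month 6 testing left. The composite is built from direct tests (working memory, reaction time, pegboard), and neither the phone questions nor the CBCL and DCDQ can replace them. The 6-month contrast for these patients then depends on MAR, which cannot be checked because their later off-drug scores are never collected. If toxicity stops are more common on everolimus, the loss is also unbalanced. A one-tailed p below .05 on this composite is enough, under section 17.1, to nominate it for Phase III.

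**Working it through.** **1. The plan's own power figure.** With 20 per arm and one-sided alpha 0.05, I used the noncentral t with df = n1 + n2 − 2 and noncentrality d × √(n1·n2/(n1 + n2)). Power is 0.799 at 0.80 SD and 0.646 at 0.65 SD, so the stated 80% and .65 reproduce. Counting only patients with a Month 6 score:

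- 2 lost per arm (10%): 0.760 and 0.605.
- 1 placebo and 6 everolimus patients lost (5% v 30%): 0.718 and 0.564.

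These overstate the loss for the planned mixed model, which also uses partial data.

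**2. Size of the possible overstatement.** Inputs from section 17.1: 20 per arm, a 0.65 SD effect of interest, a 5% v 30% dropout scenario, and correlation 0.30. My assumptions: a milder 15% v 5% scenario, correlation 0.7 as an alternative, an effect that grows linearly on drug, every stop at month 2 with the battery done then, and no effect at Months 3 and 6 once off drug. Placebo stoppers have no effect to lose, so only everolimus stops move the contrast.

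The treatment-policy effect at Month 6 (all randomized patients, on or off drug) is:

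- 15% stopping: 0.65 × 0.85 = 0.5525 SD.
- 30% stopping: 0.65 × 0.70 = 0.455 SD.

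(a) *Battery analysed at its actual date.* A stopper's two scores lie on the same on-drug line as those of completers, so the fitted line still reaches 0.65. The overstatement is 0.65 − 0.5525 = 0.0975 SD, or 0.65 − 0.455 = 0.195 SD. A simulated growth model gave 0.63–0.66.

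(b) *Battery entered as Month 6.* The month-2 score carries 0.65 × 2/6 = 0.217 SD. The contrast is 0.5525 + 0.15 × 0.217 = 0.585, or 0.455 + 0.30 × 0.217 = 0.520. The overstatement is about 0.03 or 0.065 SD.

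(c) *Off-drug Month 3 and Month 6 scores kept.* The simulated contrast was 0.55–0.56 and 0.46, close to the target.

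Simulated fits scatter around the hand values. At 30% v 5% they ran from about 0.05 SD under (b) to about 0.20 SD under (a), so I carry forward 0.03–0.10 SD (15% v 5%) and 0.05–0.20 SD (30% v 5%). The standard error of a 20 v 20 contrast is √(2/20) = 0.316 SD, so even 0.195 is 0.195/0.316 = 0.62 of a standard error.

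**3. Limits.** The illustration counts all early stops, and the six-week rule causes only some of them. A patient caught by that rule has already been off drug for about six weeks when the battery falls due, so that score is partly an off-drug score and the overstatement would be smaller. With other departures from MAR the bias could run either way, and the documents do not bound it.

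**The case against.** The best defence has four parts.

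- **Section 4.3 requires all on-site visits and makes no exception for patients off drug.** This stands. A reader might infer that nothing keeps Month 6 testing for anyone who stops early, but the documents do not support that. For stops outside the six-week rule, such as grade 4 stomatitis in Table 3, the position is unclear. The sentence does not name off-drug patients, and section 7.7.6 describes only the early visit. It cannot help a patient whom 6.3.12 has already removed.
- **Tables 3 and 4 are dosing tables, so 6.3.12 and 7.7.3 may simply add the study consequence.** That reading is possible. It removes the contradiction but leaves the loss of Month 6 data.
- **The overstatement exists only against a treatment-policy target, which the plan never states.** This is fair, and it is why the size is given relative to that target. But the plan claims intention to treat, and without off-drug data this effect cannot be estimated except by assumption.
- **The trial is exploratory and efficacy is secondary.** This is also fair. The plan predicts a difference in side-effect dropout below 10%, so 5% v 30% is a power scenario and not a forecast.

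A reader might also infer that the primary endpoint is undefined, because section 2.1 speaks of study drop-out while section 17 times medication discontinuation. The text nearly settles this: after a stop for toxicity, section 7.7.6 says "the reason for discontinuation must be recorded as due to adverse event or abnormal laboratory value". One clarifying sentence would be enough.

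**Conclusion.** The point holds and should be fixed before the analysis depends on it. Sections 6.3.12 and 7.7.3 end study participation where Tables 3 and 4 end only treatment, and the Month 6 direct testing goes with it although it could be obtained. Outside the six-week rule, off-drug visits are unclear rather than plainly dropped.

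The effect on the result is uncertain and probably modest. The ranges above rest on month-2 stops and complete loss of a 0.65 SD effect, and all lie below one standard error. They do not show that the efficacy result will be biased by a fifth of an SD. They show that the answer would depend on how one early visit is coded and on an assumption that a few retained visits would make largely unnecessary.

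The inconsistency over when the code is broken is real but subordinate. It matters mainly because retained visits need blind assessors.

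**What to change.** - **Sections 6.3.12 and 7.7.3:** replace removal from the study with permanent discontinuation of study treatment, using one six-week boundary that matches Tables 3 and 4.
- **Section 7.7.6:** state that patients off drug keep the scheduled Month 3 and Month 6 assessments unless consent is withdrawn. The early battery is an addition, analysed at its actual date.
- **Section 4.3:** amend the missed-visit termination sentence to match.
- **Blinding:** keep the testers and independent evaluators blind for these visits, and make 4.3, 4.7 and 7.6 agree on when the code is broken. Deferring participant unblinding is optional: it protects later scores, but families who stopped for toxicity would wait longer to learn the assignment.
- **Section 4.6.3:** say whether a placebo patient who stopped drug but completed Month 6 may enter open label.

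The clinical stopping rules and emergency unblinding (7.6.1) do not change.

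**Cost.** At the plan's dropout figures, 10% × 40 = 4 Month 6 visits are retained, or 1 + 6 = 7 at 5% v 30%. At the $1,500 reimbursement limit this is $6,000 to $10,500, or $12,000 to $21,000 if all also need Month 3. Testing staff time is extra and the documents do not price it. The amendment needs the review set out in section 18 (two IRBs, NIH and Novartis as applicable) and possibly re-consent under 7.2.

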7.1 Written Informed Consent

Written informed consent will be obtained from each participant before any study-specific procedures or assessments are done and after the aims, methods, anticipated benefits, and potential hazards are explained. The participant's willingness to participate in the study will be documented in writing in a consent form, which will be signed by the participant with the date of that signature indicated. The investigator will keep the original consent forms and signed copies will be given to the participants. It will also be explained to the participants that they are free to refuse entry into the study and free to withdraw from the study at any time without prejudice to future treatment.

7.2 Process of Consent

Informed consent is an ongoing process that includes the signing of an informed consent document and, when applicable, an assent form. Parents/guardians/subjects are required to sign an informed consent prior to being screened, and before undergoing any study procedures or assessments, in accordance with International Conference on Harmonization (ICH) E6; 4.8, "Informed Consent of Trial Subjects." When substantial modifications are made to the informed consent, the IRB may require that all subjects currently enrolled in the study will be re-consented; ICH E6; 4.8 guidelines would still apply. The informed consent process will be documented by the study site within the subjects' research records.

Parents/guardians/subjects will be provided with a copy of the informed consent, and assent form (if applicable), that explains the purpose of the study, the study procedures, and assessments. Parents/guardians/subjects will also be provided with the contact information of the investigator and qualified personnel who can assist with their questions and concerns.

7.3 Remote Consent Process

Remote consenting procedures will be used for re-consenting participants that are no longer coming to the research site for study related visits. Consenting by remote process should not be used for initial consent, nor for participants actively attending study visits in-clinic. Study staff will use secure methods to communicate and transmit information, such as scanning, faxing, or mailing the documents, each participant or their parent(s)/guardian(s) will be provided with two blank copies of the informed consent/assent documents: one to keep and one to return. Once the participant/parent/guardian has received the consent documents, an authorized research staff member will explain the study and review the consent document, highlighting the changes that have been made to this consent form version, with each participant by phone or videoconference. If assent is required, the authorized staff must have a discussion with both parent/legal guardian and child participant.

Once all questions have been answered and the authorized staff member feels confident that each participant/parent/guardian understands the study and the changes, the participant (adult) and/or a parent/guardian (child) will sign and date the consent form. The signed consent form will be returned to the site via email, fax, or mail. If there is a separate assent form, the participant will need to sign, date, and return the assent with the consent form. When the signed consent form is returned to the study team, the staff member who provided the explanation of the study will sign the appropriate signature line, using the current date. Please note, the site signature date should not be back-dated to coincide with the participant's signature.

It is recommended that site staff document that consent was obtained remotely, via phone or videoconference, with the current date and date the form(s) were mailed/emailed/faxed back. This can be accomplished with a note under the PI signature line on the consent form. Example: "Discussed with [patient name and parent/guardian name] via telephone/videoconference on [insert date], and received sign consent form on [insert date]."

Authorized staff should document the entire informed consent/assent process for each participant in a memo-to-file.

